6.1.1.3. Assessment of Treatment Failure

At Regulatory Agency’s request, a participant-level listing including the following variables will be provided for the ‘Dosed’ population to identify participants with treatment failure:

- (1) Participant’s Subject ID
- (2) Visit number (indicating scheduled or unscheduled)
- (3) Study Day relative to infusion day
- (4) Unconfounded FVIII activity by chromogenic assay
- (5) Description of the bleed (e.g., traumatic or spontaneous) if a bleed occurred
- (6) Reason for use of FVIII infusion if an FVIII infusion was used
- (7) Study Day of prophylaxis resumption
- (8) Reason of prophylaxis resumption

Unconfounded FVIII activity data are the appropriate FVIII activity data that are collected beyond 72 hours after administering FVIII infusion with standard half-life or 120 hours with extended half-life. This data listing will include a row when there is an occurrence in any of the variables in (4), (5), (6) and (7). The last row for each participant will include the Study Day on data cutoff for the given participant. Clinical review will be conducted using this listing to identify participants with treatment failure.

6.2. Secondary Endpoints

6.2.1. Key Secondary Endpoint: FVIII Activity Level > 5%

6.2.1.1. Main Analysis

The percentage of participants with FVIII activity level > 5% at 15 months postinfusion will be tested against the null hypothesis of percentage $\leq 68\%$ using a one-sided exact binomial proportion test at one-sided alpha = 0.025 using the ‘Efficacy’ population. The number of participants in the analysis population, number of participants with FVIII activity level > 5%, percentage with the 95% CI of the percentage, and p-value will be provided.

Participants who prematurely discontinue from the study or resume prophylaxis regimen prior to reaching Month 15 visit will be considered as having FVIII activity $\leq 5\%$ for this percentage assessment.

The 15 months postinfusion is corresponding to a study visit at Week 65. Any appropriate FVIII activity data collected at unscheduled visits during Week 63 to Week 67 (i.e., the visit window for Week 65 visit) will be included in this assessment. Imputation rules as described in [Section 3.2.1](#) will be applied.

6.2.1.2. Sensitivity/Supplementary Analysis

The number (%) of participants achieving specific FVIII activity intervals via CA and OS assays separately (e.g., <1%, 1-5%, >5-<15%, 15-<40%, 40-<150%, >150%) at Week 12, Week 26 (Month 6), Week 52 (Month 12), Month 15, Month 18, Year 2, Year 3, Year 4, and Year 5 postinfusion will be summarized separately for the ‘Dosed’ population. For visualization, a stacked bar chart will be generated, presenting percentage of participants achieving specific FVIII activity thresholds via CA and OS assays mentioned above at the given time points based on the ‘Dosed’ population.

The number of participants present at the beginning of each protocol-defined visit window will be used as the denominator for percentage calculation. Imputation rules as described in [Section 3.2.5](#) will be applied.

6.2.2. Key Secondary Endpoint: Treated ABR

6.2.2.1. Main Analysis

Treated ABR from Week 12 [Day 78] through at least 15 months (up to data cutoff) post PF-07055480 infusion will be analyzed using the same main analysis method as for Total ABR on the ‘Efficacy’ population.

6.2.2.2. Sensitivity/Supplementary Analysis

The following sensitivity analyses will be conducted:

- For completeness, the same analysis model and summary used for the main analysis will be repeated for the Treated ABR from Week 12 through data cutoff, using the ‘Dosed’ population (regardless of the length of follow-up in preinfusion or postinfusion).

- Same analysis as described for the main analysis will be performed on the Treated ABR from Week 12 through data cutoff, using the ‘Evaluable’ population if it is different from the ‘Dosed’ population.

As supplementary analyses, Treated ABR by yearly interval and by cumulative follow-up interval post PF-07055480 infusion are considered as secondary endpoints and will be analyzed using the same analysis model and summary as for the main analysis of Total ABR (using the ‘Efficacy’ population).

No other sensitivity/supplementary analyses will be conducted.

6.2.3. AIR of Exogenous FVIII

6.2.3.1. Main Analysis

AIR of exogenous FVIII from Week 12 [Day 78] through at least 15 months (up to data cutoff) post PF-07055480 infusion vs AIR during FVIII prophylaxis replacement regimen will be tested with a paired t-test for superiority to demonstrate the reduction of overall burden in the participants.

- The ‘Efficacy’ population will be the main analysis population for the primary analysis.
- The summary table will include two columns, for FVIII prophylaxis (pre PF-07055480) and PF-07055480 (post PF-07055480), respectively. The descriptive statistics including number of participants (n), mean, median, Q1, Q3, min, max of the observed AIR, mean difference of (AIR PF-07055480 – AIR FVIII prophylaxis), and the 95% CI of the mean difference will be presented in the summary table. In addition, the p-value from the paired t-test will be provided. The percent reduction in mean AIR will be derived as $100 * [1 - (\text{mean AIR PF-07055480}) / (\text{mean AIR FVIII prophylaxis})]$.

6.2.3.2. Sensitivity/Supplementary Analysis

The following sensitivity analyses will be conducted:

- The same analysis and summary as described above will be repeated for the AIR from Week 12 through data cutoff, using the ‘Dosed’ population (regardless of the length of follow-up preinfusion or postinfusion).
- To include only the data collected in the lead-in study (C0371004) (i.e., excluding the preinfusion data in C3731003) and the data postinfusion of PF-07055480 using the same analysis model as the main analysis. This analysis will be conducted on the ‘Efficacy’ population.

As supplementary analyses, AIR in yearly intervals, as well as AIR in cumulative follow-up intervals (i.e., from Week 12 through 2 years postinfusion, from Week 12 through 3 years postinfusion, etc.) as defined in [Section 3.1.1](#), will be tested separately with the same method

as for the main analysis using the ‘Efficacy’ population to demonstrate superiority over AIR of FVIII prophylaxis replacement regimen as secondary endpoints.

In addition, percentage of participants who have resumed prophylaxis regimen and descriptive statistics for the time to prophylaxis resumption will be reported for the above-mentioned time periods (i.e., from Week 12 through data cutoff, by yearly interval, and by cumulative follow-up interval) in the ‘Efficacy’ population and the ‘Dosed’ population separately.

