	
compared with prior FVIII prophylaxis replacement regimen:
 
 • Annualized FVIII consumption. • Treated ABR of specific type: 
 ◦ by cause (spontaneous or traumatic) ◦ by location (in joints, in target joints, or in soft tissue). • Total ABR by cause and by location. • Percentage of participants without bleeds. 
The following secondary parameters will be assessed by visit after PF-07055480 infusion:
 
 • FVIII activity level. • Change from baseline in joint health as measured by the Hemophilia Joint Health Score (HJHS) instrument. • Change from baseline in the following PRO endpoints: 
 ◦ Haemophilia Quality of Life Questionnaire for Adults (Haem-A-QoL) ◦ Haemophilia Activities List (HAL)

 • Estimate the durability of efficacy up to 5 years after PF-07055480 infusion. 	
The following parameters will be analyzed yearly or by visit as appropriate:
 
 • Treated ABR. • FVIII activity level. • AIR of exogenous FVIII. • Annualized FVIII consumption. • Treated ABR of specific type: 
 ◦ by cause (spontaneous or traumatic).

Objectives	Endpoints
	
 ○ by location (in joint, in target joints, or in soft tissue). ● Total ABR. ● Total ABR by cause and by location. ● Percentage of participants without bleeds. ● Change from baseline in joint health as measured by the HJHS instrument. ● Change from baseline in PRO endpoints: Haem-A-QoL and HAL. 
In addition, Treated ABR, Total ABR, and AIR will be analyzed throughout the 5-year study period.

Secondary Safety Objective	Secondary Safety Endpoints

 ● To estimate the safety and tolerability of PF-07055480, including immunogenicity, for the study duration of 5 years after PF-07055480 infusion. 	
 ● Incidence and severity of adverse events (AEs). ● Events of special interest (such as hypersensitivity reactions, clinically reported thrombotic events, and malignancy). ● Immunogenicity: 
 ○ Antibodies against adeno associated viral vector, serotype 6 (AAV6) capsid protein (neutralizing antibodies [nAbs] and anti-drug antibodies [ADAs]). ○ T-cell responses against AAV6 capsid and against the transgene. ○ FVIII inhibitors.
Tertiary/Exploratory	

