3.2.5. FVIII Activity Level by Visit

Mapping for unscheduled visit observations and exclusion in FVIII activity data are described in [Section 3.2.1](#). FVIII activity analyzed by the central laboratory will be reported for chromogenic assay and one-state clotting assay separately. FVIII activity will be imputed with 0.9% through data cutoff after the participants have resumed prophylaxis regimen and after they discontinued from the study due to lack of efficacy. FVIII activity won't be imputed after participants discontinue from the study due to reasons other than lack of efficacy if they have not resumed prophylaxis. Specifically, imputation of FVIII activity will be applied per scenarios listed below:

- Resumed prophylaxis but remained in the study: Impute FVIII activity with 0.9% at any protocol-defined visits post resumption of prophylaxis until data cutoff.
- Resumed prophylaxis and then discontinued from the study due to any reasons: Impute FVIII activity with 0.9% at any protocol-defined visits post resumption of prophylaxis until data cutoff.
- Discontinued from study due to lack of efficacy but has not resumed prophylaxis: Impute FVIII activity with 0.9% at any protocol-defined visits post study discontinuation until data cutoff.
- Discontinued from the study due to any reasons other than lack of efficacy but has not resumed prophylaxis: No imputation will be applied. FVIII activity after study discontinuation will be considered missing.

FVIII activity levels by visit will be summarized. In addition, the percentage of participants with FVIII activity level $\geq 40\%$ will be reported by visit up to data cutoff.

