4. ANALYSIS SETS (POPULATIONS FOR ANALYSIS)

For purposes of analysis, the following populations are defined:

Population	Description	Applicable Analysis (for additional information refer to Section 6)
Enrolled	All participants who sign the informed consent form (ICF) and meet all inclusion/exclusion criteria.	Disposition events summary
Dosed/Safety	All participants enrolled in the study and who receive the study intervention.	Demographic and baseline characteristics, hemophilia history, medical history, safety, nAbs, ADA, FVIII antigen, von Willebrand factor, vector shedding assessments, joint health assessments, efficacy sensitivity/supplementary analyses, PRO analyses, and coagulation activation tests.
Evaluable	
All participants enrolled in the study and who receive the study intervention and have no significant interruption of efficacy measurement.
 
The ‘Evaluable’ analysis population will include participants who receive the study intervention (full dose of infusion) and exclude participants with significant interruption of efficacy measurement. The significant interruption would occur if the participant discontinues from the study, is lost to follow-up, has significant
	Efficacy sensitivity/supplementary analyses

Population	Description	Applicable Analysis (for additional information refer to Section 6)
	interruption in data collection, or has a major protocol deviation.	
Efficacy	All participants in the 'Dosed' population who have completed at least 6 months of follow up in the lead-in study and at least 15 months of follow up or discontinued from the study C3731003 prior to the data cutoff for reporting.	Main analysis population for efficacy
Ultrasound Substudy	All participants who sign the additional ICF for the ultrasound substudy and meet all inclusion/exclusion criteria, and the participant's joint ultrasound have been reviewed following the extended ultrasound scale at baseline, and any data post-baseline.	HEAD-US ultrasound scale - total score and subscores, demographic and baseline characteristics, AEs, disposition, and FVIII activity level data.
Vector Shedding Substudy	All participants who sign the additional ICF for the Vector Shedding substudy and meet all inclusion/exclusion criteria, and who provide any additional vector shedding data for analysis.	Shedding vector levels in PBMC, saliva, urine, semen, and plasma; demographic and baseline characteristics, AEs, disposition, and FVIII activity level data.

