5.2.2. Analyses for Continuous Endpoints

The n, mean, median, standard deviation, Q1, Q3, minimum (min), maximum (max), and 95% CI of mean (when appropriate) for the observed value and the change from baseline by visit will be provided in the summary tables.

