Total ABR postinfusion (from Week 12 through at least 15 months [up to data cutoff] postinfusion of PF-07055480) with imputation	US-specific analysis: supplementary	Efficacy	Same as for the main analysis and the imputation rules described in Table 10 will be applied.	Same as for the main analysis with hypothesis testing.
Assessment of treatment failure	Primary analysis: supplementary analysis	Dosed	Details are described in Section 6.1.1.3.	Participant-level data listing.
FVIII activity level > 5% at 15 months postinfusion of PF-07055480	Primary analysis: main analysis	Efficacy	
 Any sample taken within 72 hours after administering standard half-life exogenous FVIII replacement therapy, or 120 hours for products with extended half-life, for any purpose (including treatment of bleeding or prevention purposes) will be excluded. Participants who resume prophylaxis regimen prior to reaching Month 15 visit will be considered as having FVIII activity level $\leq 5\%$. Participants who discontinue from the study prior to reaching Month 15 visit will be considered as having FVIII activity level $\leq 5\%$. Missing FVIII activity level will be imputed with the earliest FVIII level collected post Week 65 (Month 15) visit 	Exact test for binomial proportion

Endpoint	Analysis Type	Population	Data Inclusion and Rules for Handling Intercurrent Events and Missing Data	Analysis
			window. In case there are no FVIII activity levels collected post Week 65 visit window but the participant has not discontinued from the study, the FVIII activity level will be considered as missing and excluded from the analysis.	
FVIII activity level <1%, 1-5%, >5-<15%, 15-<40%, 40-<150%, >150% at Week 12, Week 26 (Month 6), Week 52 (Month 12), Month 15, Month 18, Year 2, Year 3 postinfusion	Primary analysis: sensitivity analysis	Dosed	See imputation rules described in Section 3.2.5 .	Number (%) of participants
Treated ABR (from Week 12 through at least 15 months [up to data cutoff] postinfusion of PF-07055480)	Primary analysis: main analysis	Efficacy	
 Any data after the resumption of FVIII prophylaxis regimen (if necessary) will be excluded. Data after study discontinuation will not be imputed. 	Same as above for Total ABR from Week 12 through at least 15 months (up to data cutoff).

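### The planned summary of prophylaxis resumption is not adjusted for unequal follow-up, so its later intervals at the primary analysis can understate the risk; a censored cumulative incidence estimate should be added.

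*SAP*

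**What the plan says.** The summary is a supplementary item under annualized infusion rate (SAP 6.2.3.2). It promises that the "percentage of participants who have resumed prophylaxis regimen and descriptive statistics for the time to prophylaxis resumption will be reported" for three kinds of period ("from Week 12 through data cutoff, by yearly interval, and by cumulative follow-up interval"), in the Efficacy and Dosed populations separately. SAP 5.2.2 defines descriptive statistics for continuous variables as n, mean, median, standard deviation, quartiles, range and a confidence interval for the mean. The SAP contains no Kaplan-Meier or cumulative incidence estimate. The item is missing from the SAP Appendix 2 table, so nothing there fills in the detail.

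Follow-up differs between participants. The Efficacy population requires "at least 15 months of follow up or discontinued from the study C3731003 prior to the data cutoff for reporting", plus 6 months in the lead-in study. The Dosed population is "All participants enrolled in the study and who receive the study intervention", with no minimum. SAP Appendix 2 schedules FVIII activity categories for the primary analysis at time points that include "Week 52 (Month 12), Month 15, Month 18, Year 2, Year 3 postinfusion", so some participants are expected to have about three years by then.

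One secondary objective is to "Estimate the durability of efficacy up to 5 years after PF-07055480 infusion" (SAP 2.2). For FVIII activity by visit, SAP 3.2.5 has an explicit rule for the case "Discontinued from study due to lack of efficacy but has not resumed prophylaxis": impute 0.9% afterwards. SAP 6.2.3.2 has no matching rule.

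**The concern.** A percentage of all participants, taken over unequal follow-up, mixes people observed for the whole interval with people observed for part of it. Someone cut off at 16 months counts as a non-resumer through 3 years, and so does someone who left the study before resuming. A mean or median time with no censoring rule can use only participants with an observed time, that is, those who resumed. The SAP does not say this in words, but it is the natural reading of the plan. Such a time mainly reflects how long people were followed.

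What is at stake is how the later bleeding results are read. The primary estimand excludes data after resumption (SAP 2.2.1), and yearly Total ABR leaves out anyone who resumed or discontinued before the interval began (SAP 6.1.1.2). Later-year ABR therefore describes participants still off prophylaxis. A reader needs a sound estimate of how many were removed and when.

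**Working it through.** The SAP states no figure to reproduce here. The check asks how far a crude percentage over all participants falls below the true risk.

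**Inputs.** From the documents: minimum follow-up of 15 months (1.25 years) in Efficacy, none in Dosed, and about 3 years or more for the longest-followed participants. Assumed, not in the documents: constant resumption rate h per year from infusion; follow-up uniform from a to b years, independent of resumption; a = 1.25 (Efficacy-like) or 0.25 (Dosed-like); b = 3.5; no dropout. Starting the summary at Week 12 is ignored.

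**Formula.** For an interval from infusion to H years, with H between a and b:

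crude = 1 − { [e^(−ha) − e^(−hH)]/h + (b − H)e^(−hH) } / (b − a); true risk = 1 − e^(−hH).

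**Efficacy-like set, h = 0.10** (e^(−0.125) = 0.8825, e^(−0.2) = 0.8187, e^(−0.3) = 0.7408):
- Month 15: crude = true = 1 − 0.8825 = 11.8%.
- 2 years: 1 − [0.6377 + 1.5 × 0.8187]/2.25 = 17.1%; true 18.1%.
- 3 years: 1 − [1.4168 + 0.5 × 0.7408]/2.25 = 20.6%; true 25.9%.

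**Through 3 years, by rate:**

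| h per year | True | Crude, Efficacy-like | Crude, Dosed-like |
|---|---|---|---|
| 0.05 | 13.9% | 10.9% | 8.7% |
| 0.10 | 25.9% | 20.6% | 16.5% |
| 0.15 | 36.2% | 29.1% | 23.4% |

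In the Dosed-like set a gap exists already at Month 15: 1 − [0.9281 + 2.25 × 0.8825]/3.25 = 10.3% against 11.8%.

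**Time among resumers.** To cutoff, in the Efficacy-like set, the mean time is 1.24, 1.21 and 1.18 years at h = 0.05, 0.10 and 0.15. The rate triples and the mean barely moves.

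**Second set of assumptions.** Follow-up uniform over 15 to 36 months (Efficacy) or 3 to 36 months (Dosed), with monthly rate L = −ln(1 − p)/36 for a true 36-month risk p. For p = 10%, crude = 1 − [e^(−15L) − e^(−36L)]/(21L) = 7.2% in Efficacy; starting from 3 months, with divisor 33L, it is 5.5% in Dosed. In simulation with 50 participants, the median time among resumers was about 13 months, against a true median of 237 months, and 1 minus Kaplan-Meier averaged 10.0%. With 3% annual dropout, the shortfall to Month 15 in Efficacy was at most 0.2 points.

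**Final analysis.** Everyone has 5 years or has discontinued, so only dropout matters. With monthly dropout rate d, crude = L/(L + d) × [1 − e^(−60(L + d))]. For dropout of 3% and 5% a year, crude is 15.0% and 14.3% against a true 16.1% (p = 10%), and 28.9% and 27.6% against 31.1% (p = 20%).

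**The case against.** The strongest reply is that the SAP already reports by yearly and cumulative interval. If the yearly percentages use those still at risk at the start of the interval, as yearly ABR does, they come close to a life table. This stands in part: it limits the problem, and the unstated denominator means the plan might be better than it looks. It does not remove the problem in an interval still in progress at cutoff. In the Efficacy-like set with h = 0.10, follow-up within Year 3 among those at risk at 2 years is uniform over 0 to 1.5 years. The percentage is then 1 − [(1 − e^(−0.1))/0.1 + 0.5e^(−0.1)]/1.5 = 1 − [0.9516 + 0.4524]/1.5 = 6.4%, against a true 9.5%.

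Three stronger readings are tempting, and the documents do not support them.
- A reader might take this summary as the main measure of loss of efficacy. It is supplementary, and SAP 2.2 does not list it among the durability endpoints.
- A reader might take resumption as the study's definition of treatment not being efficacious. Protocol 6.5.1 defines that by FVIII activity or spontaneous bleeds; resumption is what a participant may then do. SAP 6.1.1.3 handles treatment failure separately, by listing and clinical review.
- A reader might conclude that the plan as a whole hides failure or cannot show durability. Resumption counts as FVIII activity of 5% or less in the key secondary endpoint, as 0.9% in FVIII activity by visit, through its infusions in the infusion rate, and as a Total ABR of 35 in the US-specific analyses.

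None of those analyses, however, estimates the probability of remaining off prophylaxis over time.

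**Conclusion.** The point holds in a limited form. SAP 6.2.3.2 plans no censored estimate for time to resumption and leaves the denominator, time origin and handling of discontinuation open. If all participants form the denominator, the understatement at the primary analysis falls chiefly in the 3-year interval: about 3 to 7 points in an Efficacy-like set and 5 to 13 points in a Dosed-like set, for assumed rates of 0.05 to 0.15 per year. It is about 1 point at 2 years in the Efficacy-like set at 0.10 per year, and nil to Month 15 there without dropout. At the final analysis it arises only from dropout, at roughly 1 to 3.5 points under the dropout rates tried. The direction follows from the design; the sizes rest on assumed rates and follow-up patterns. Alpha, power, sample size and the primary test are untouched. This is an inexpensive improvement to a supplementary analysis that helps the reader interpret later-year ABR.

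**What to change.** Keep the planned summary and state the denominator for each interval and the time origin. Add a cumulative incidence estimate of time from infusion (Day 1) to prophylaxis resumption in the Dosed population:
- Count discontinuation for lack of efficacy as an event, in line with SAP 3.2.5.
- Censor at data cutoff or at discontinuation for other reasons.
- Treat death as a competing event and use the Aalen-Johansen estimator. It equals 1 minus Kaplan-Meier if no deaths occur; otherwise the two differ, so the SAP should name the estimator.
- Report yearly estimates with 95% confidence intervals and numbers at risk, as far as follow-up supports at the primary analysis and through 5 years at the final analysis.

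List the analysis in SAP Appendix 2. The cost is one table and one figure from data already collected, since SAP 2.2.1 records the date and reason of resumption in the eCRF.
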